9.0 STUDY INTERVENTION

9.1 Study Intervention Description

The device used for this intervention will be the Soterix 1x1 Limited Total Energy tDCS Stimulator Model 1401.

With IRB approvals and FDA IDE exemptions, we have safely and feasibly used the Soterix LTE tDCS model over the last decade. Previous IRB approval has been obtained using an FDA IDE exemption with NSR status (see FDA letter/[name]). The Soterix LTE tDCS model will be used to deliver low-intensity tDCS in the home setting, to children with CP assisted by the parent/legal guardian and monitored by the safety monitor team member – henceforth referred together as the ‘participant team’ - and with synchronous remote instruction by the investigative team. The procedure will target the primary motor

cortex (M1) using a bilateral M1 electrode montage. The M1 is a cortical area of interest for interventions aimed at improving motor skills in our participant population who have hemiparetic cerebral palsy with perinatal stroke and brain bleed, and as is conventional using this montage, we will place the anode over the lesioned or more-involved hemisphere. We intend to deliver tDCS in three active sessions, at a current intensity of 1.5 mA (based on child tolerance) and 20 min duration in each of the three active stimulation sessions.

9.1.1 Source

Soterix Medical will distribute LTE Transcranial Direct Current Stimulator to the study site. The contents of the shipment will then be reviewed and verified against the packing slip and will be documented as instructed at the initiation visit.

Soterix Medical Inc.
Aspen Corporate Park,
[name]
Email: [contact] [contact]
[contact]

The study team will be responsible for procuring the LTE tDCS stimulator.

9.1.2 Packaging and Labeling

Device installation and maintenance will follow manufacturers' instructions for approved use. The device will be delivered by the safety monitor study team member to the participant.

9.1.3 Storage and Stability

Investigational product must be stored in a secure area accessible only to authorized trial personnel. When not out at participants' homes, the device will be installed and housed in the Pediatric Neuromodulation Laboratory, in a dedicated and locked research space, accessible only by/with authorized study team personnel. The Pediatric Neuromodulation Laboratory is located within the Waisman Center, and the facility meets all the requirements needed for appropriate installation, functioning, and storage of the device following manufacturer's instructions. The device must be stored away from fluids and heat sources. The storage temperature of the device must be between 50°F - 80°F with a maximum humidity of 70%. The temperature must be monitored and documented on the appropriate form for the entire time that the investigational product is at the trial site. If the storage temperature deviates from the permitted range, the investigational product must not be administered, and the site investigator or responsible person should contact Soterix Medical for further instructions. The device will also follow these precautions and warnings:

- *The Soterix Medical LTE tDCS Stimulator must be stored away from fluids and heat sources.*
- *To clean the Soterix Medical LTE tDCS Stimulator, use a dry cloth to wipe dust from the external surface when necessary. Do not spray liquid cleaners directly on the Soterix Medical LTE tDCS Stimulator, as this will void your warranty.*
- *Do not disinfect the Soterix Medical LTE tDCS Stimulator*
- *Do not immerse the Soterix Medical LTE tDCS Stimulator in water or any other fluids.*
- *The Soterix Medical LTE tDCS Stimulator should not be used in a moist environment or if any parts of the stimulator are damp or wet.*
- *Do not drop the device.*
- *The Soterix Medical LTE tDCS Stimulator should not be used if there are any signs of external damage.*
- *Carefully inspect the device on arrival and prior to each use.*

- *If any controls or displays are not working as indicated in the manual. Immediately return the device to Soterix Medical Inc. for repair.*
- *Storage and operation temperature must be between 50° F and 110° F*

At the start of each experimental session, the investigative team will carefully inspect the device, together with the participant team, via video conference.

9.1.4 Accountability

The study coordinator will maintain records of product delivery, site inventory, and product return. The safety monitor will be responsible for bringing the device to the participants home for every session and taking it after completing the session.

In the event of a quality issue, the site should quarantine the investigational product and contact Soterix Medical for further instructions.

9.1.5 Dosing and Administration

tDCS stimulation will be delivered at 1.5mA for 20 minutes while the caregiver and study team members evaluate the participant for any potential adverse event. Refer to the adverse events section below for more information. If it is uncomfortable to go to the full intensity, we will adapt and modify the stimulation to 1.0 mA by adjusting the device's dial in person by the caregiver or safety monitor as directed by the study coordinator.

9.2 Study Procedural Intervention(s) Description

9.2.1 Administration of Procedural Intervention

Active tDCS stimulation will be delivered to the participants during sessions 3-5 of the study after participants have been evaluated and cleared for quality set-up of the tDCS montage. A trained study team member will interact virtually with the caregiver to activate the tDCS stimulation device while a safety monitor team member will be located in person to supervise any safety concerns.

9.3 Method for Assigning to Treatment Groups

This is an open label study; there are no blinding procedures.

9.4 Study Intervention Compliance

Protocol compliance will be assessed directly by trained lab members. The lab team will witness and monitor the activation of the LTE device by the trained caregiver. The caregiver administering stimulation must be the individual who was successfully trained during the practice sessions. The safety supervision lab member will assess any safety concerns throughout the process at the site of the stimulation.

9.5 Concomitant Therapy

9.5.1 Permitted Concomitant Therapy

Concomitant therapies and medication are permitted and will be documented during the screening visit. This is not expected to affect the primary or secondary outcome measures of the study.

9.5.2 Prohibited Concomitant Therapy

Concomitant participation in another neuromodulation study is prohibited considering concurrent neuromodulation may directly affect the endpoints of the study. Additionally, participants who received Botulinum toxin or phenol block within the last six months preceding the study are prohibited from participating. However, after completion of the tDCS stimulation sessions, participants will be eligible to

participate in the optional 6 month/12-month visits as long as they have participated in the study before and have access to working internet and computer/laptop/device.

10.0 STUDY VISITS AND PROCEDURES

10.1 Study Calendar

The procedures performed at each study visit are listed in the table below.

Procedure	Screening	Session 1	Session 2	Active stimulation Session 3-5	1 week post day 5 completion
Informed Consent	X				
Review Eligibility Criteria	X				
Obtain Medical History	X				
Vitals Measured			X	X	
Stimulation montage setup		X	X	X	
Setup ease/comfort survey		X	X	X	
Safety Monitor Present In-home (active device use)			X	X	
Motor Behavior Assessment ¹ pre, post stimulation			X	X	
Adverse Events Survey pre, during, post stimulation		X	X	X	
Device stimulation administration			Sham	Active	
Follow-up					X

Procedure	Optional 6-month/12-month follow up
Informed Consent/Assent	X
Obtain Medical History	X
Motor Behavior Assessment ¹	X
Surveys ²	X

¹ Box and Blocks Test

² Gross Motor Function Classification System, Pediatric Cognition Survey, Current Therapy survey, Demographic Survey, tDCS Tolerance Survey, tDCS Subject Report of Symptoms Questionnaire

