6.1 Aims

Aim 1. Determine the safety and tolerability of 20 minutes of at-home active tDCS with remote instruction.

Hypothesis 1: Children will tolerate the stimulation well with no serious adverse effects.

Hypothesis 2: The repeated and guided sessions will result in increased comfort and confidence reported by the caregivers and children in performing tDCS at home.

Aim 2. Determine the feasibility of remotely instructed teleneuromodulation with active tDCS.

Hypothesis 1: Based on our preliminary feasibility study, we expect caregivers and children to correctly and reliably setup a stimulation montage with children after following remote instructions over two practice sessions.

Hypothesis 2: Participants will be able to initiate and successfully complete active tDCS over repeated sessions, with increasing quality of stimulation delivery.

Exploratory Aim 3 - Integrate feedback from the child and caregivers to assess their interest or commitment to engaging in future at-home tDCS interventions towards the construct of an advanced clinical trial.

Hypothesis 1: The majority of families will express interest in future participation.

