8.7 Early Termination and Withdrawal

Families are free to withdraw from participation in the study at any time upon request.

The Principal Investigator (PI) may discontinue or withdraw a subject from the study for the following reasons at his/her discretion:

- Legal guardian/parent of the child voluntarily withdraw from the study
- Participant death
- Pregnancy
- Subject non-compliance with study requirements (e.g., study intervention non-compliance)
- If any clinical adverse event (AE), laboratory abnormality, or other medical condition or situation occurs such that continued participation in the study would not be in the best interest of the subject
- If the subject is no longer an appropriate candidate for participation
- There is evidence of progressive disease or unacceptable toxicity
- Subject unable to complete the 5 sessions within two weeks

Participants withdrawn from study will be replaced, and the details surrounding the circumstances for withdrawing the participant from the study will be reported, with no identifiers included. Data collected up to the point of withdrawal will be kept and used for analysis. Participants who withdraw from the study will be given the opportunity to be involved in the 6-month/12-month follow up study visits.

If the study ends prior to the study completion, all scheduled participants and families will be notified, and study sessions will be terminated. All research investigators on the study will be notified. The funding agency will also be notified.

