10.2.5 Adverse events survey

Tolerance and report of any symptoms will be formally assessed using tDCS-specific participant safety questionnaires. This includes common mild effects like skin tingling and itching, as well as others such

as headache, anxiety and mood changes, or any other events. This survey is filled out before, during at the 10-minute mark, and after tDCS stimulation sessions 1-5.

10.2.6 1-week Follow-up

We will ask the participants an open-ended question to check-in, assess the family's experience with the overall procedure and potential interest in future studies. This will be called the tDCS tolerance survey. This will occur via telephone one week after completion of the session.

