10.10 Study Stopping Rules

Both Individual and Entire Study stopping rules are described below:

Death. Study stopped for both individual and entire study. A full investigation of event will be explored by entire study team. The medical monitor will review all details. Report of event will be distributed to all governing and monitoring committees.

Seizure: Individual- Immediate suspension of tDCS application for this particular child and initiation and follow-through of safe and effective seizure management. Refer to seizure management outline. Provide physician letter to subject which describes the research-related adverse event with physician interpretation.

Pregnancy: If at any time during the study, the participant states that they are pregnant, the participation will not be allowed to continue within the primary study. They will be allowed to participate in the 6 and 12-month follow up visits as described in 14.6 Reporting of Pregnancy.

Transient Decline in Motor Function (Individual). Immediate suspension of TMS intervention for the particular participant and initiation of assessment of the change. A written report with detailed documentation of decline in function will be submitted to the Medical Monitor. The participant's pediatrician and neurologist will also be contacted. Follow-up testing will then occur one week after suspension of the study to track progress and change in status with physicians contacted with results directly thereafter.

Transient Decline in Motor Function (Entire Trial). If any participant shows a decrease in function following any component of the proposed study (tDCS or behavioral assessment), the study will be stopped at that time for review by the Medical Monitor. If the Medical Monitor deems that the change in function does not indicate need for termination of the study, the study will recommence. If the Medical Monitor deems that the protocol has indications for change, the study will be reviewed by the investigative team, including consultants and will be changed and submitted for re-approval by the IRB before recommencing the study.

Entire Study- If another subject incurs a seizure proceed with steps for Individual Stopping Rules as noted above. Study will be suspended at this point and a thorough review by research team, medical monitor and consultants will occur in order to assess the need for amendment of the protocol or full stop/termination of study for future safety concerns.

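### The 1-week call is tied to finishing day 5, so the 1-week feedback and the exploratory Aim 3 interest result would come from completers only

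*Combined protocol and SAP*

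**What the plan says.** The calendar in section 10.1 has a single follow-up column before the optional 6- and 12-month visits, headed "1 week post day 5 completion". It has no column for a child who stops early.

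Section 10.2.6 describes the contact as an open-ended enquiry into the family's "experience with the overall procedure and potential interest in future studies", and adds: "This will be called the tDCS tolerance survey". On timing it says: "This will occur via telephone one week after completion of the session". It does not say which session is meant. Section 7.2 makes this call one of the conditions for having completed the primary study.

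The interest answer bears on exploratory Aim 3 (section 6.1), whose hypothesis is: "The majority of families will express interest in future participation". No denominator is given.

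Section 8.7 replaces participants who are withdrawn, offers them the optional 6- and 12-month visits, and says: "Data collected up to the point of withdrawal will be kept and used for analysis". It does not mention the 1-week call. Section 10.10 provides a one-week contact after one kind of early stop, a transient decline in motor function: "Follow-up testing will then occur one week after suspension of the study to track progress and change in status".

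Tolerability is also measured elsewhere. Section 10.2.5 says: "Tolerance and report of any symptoms will be formally assessed using tDCS-specific participant safety questionnaires". Those questionnaires are completed before, during and after each of sessions 1 to 5.

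**The concern.** A child who stops at session 2, 3 or 4 never reaches the calendar's anchor. Early stopping is foreseen: section 8.6 prorates payment for it, and section 8.7 lists adverse events and failure to finish five sessions within two weeks as grounds for withdrawal. Because such a child is replaced, the trial can still report ten 1-week calls, all from families who finished.

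Two things are at stake. First, families who stopped early may well be less interested in taking part again, so an interest proportion among completers could be too favourable. Section 5.3 says the feedback is meant to inform the design of a larger study. Second, the session questionnaires end with the last session attended. For an early stopper they cannot show whether a symptom later resolved or whether a new one appeared, and the next routine enquiry is an optional visit months later.

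**Working it through.** **Passages side by side**

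| Item | Early stoppers included? | Source |
|---|---|---|
| Adverse event survey at each session attended | Yes, up to the last session | 3.1, 10.2.5 |
| Adverse event frequency | Yes, percentage of all enrolled | 3.1 |
| Data collected before withdrawal | Yes, kept and analysed | 8.7 |
| 1-week tolerance survey | Not scheduled under the calendar; unclear under 10.2.6 | 10.1, 10.2.6 |
| Interest in future studies (Aim 3) | Same call, so the same gap | 6.1, 10.2.6 |
| One-week motor retest | Only after motor decline; motor status only | 10.10 |
| Tolerance survey and symptom interview at 6 and 12 months | Offered, but optional and late | 8.7, 10.2.7 |

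The gap is therefore confined to the two 1-week results and to routine symptom enquiry between the last session and month 6.

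**Size of the effect on the interest proportion**

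The plan states no figure to reproduce. Suppose 10 children complete, x of their families are interested, and k further children stopped early, were replaced and were not called. Over all who started, the proportion lies between x/(10 + k), if no stopper is interested, and (x + k)/(10 + k), if all are. Both x and k are assumptions.

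| x | Completers only | k = 1 | k = 2 |
|---|---|---|---|
| 6 | 6/10 = 60% | 6/11 = 55% to 7/11 = 64% | 6/12 = 50% to 8/12 = 67% |
| 7 | 7/10 = 70% | 7/11 = 64% to 8/11 = 73% | 7/12 = 58% to 9/12 = 75% |

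At x = 6 and k = 2 the lower bound is exactly half, which is not a majority. In the other cases shown a majority remains.

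**How likely early stops are**

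Section 8.5 reports 100% retention in 50 children, that is 0 of 50 lost. The exact upper confidence limit for the loss rate is:
- one-sided 95%: 1 − 0.05^(1/50) = 5.8%
- two-sided 95%: 1 − 0.025^(1/50) = 7.1%

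Among the first 10 children, with independent stops at rate d, the chance of at least one early stop is 1 − (1 − d)^10. The chance of two or more subtracts 10d(1 − d)^9 from that.

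| d | At least one | Two or more |
|---|---|---|
| 2% (assumed) | 18% | 1.6% |
| 5.8% | 45% | 11% |
| 7.1% | 52% | 16% |
| 10% (assumed) | 65% | 26% |

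If past retention recurs exactly, k = 0 and nothing changes.

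**The case against.** A reader might infer that the trial's tolerability result as a whole comes from completers. The documents do not support that. The primary endpoint in section 3.1 is the per-session adverse event survey with the Box and Blocks test, the frequency denominator is all enrolled, and withdrawn children's data are kept. The 1-week contact is one open-ended question, and section 6.0 lists follow-up feedback as correlative/exploratory.

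Nor do the documents say that whoever tolerates stimulation badly is lost. Section 10.2.1 provides for stopping after a mild event, reassessment, and possible adjustment for later sessions, so some of these children may finish and receive the call. Section 8.7 does not state that stopping stimulation is the same as leaving the study. Section 10.8 has both the family and the study team report events arising after any session, so later symptoms are not left wholly to chance. These points stand. What is missing is routine, scheduled enquiry for early stoppers.

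It can also be said that the call may be provided for in text not supplied. The contents list names an Early Termination/Withdrawal Visit and sections on event follow-up and missing data, none of which is in the supplied body, and section 10.3.7 breaks off mid-sentence. The wording of 10.2.6 could also cover an early last session. The absence is therefore not certain, but the calendar that is present shows no such contact and disagrees with 10.2.6.

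Finally, Aim 3 is exploratory, past retention was complete, and losing the majority needs a borderline result and at least two uninterested stoppers. That is fair, and it limits the weight of the numerical example.

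**Conclusion.** The point holds in limited form. Followed as the calendar is written, the 1-week tolerance feedback and the Aim 3 interest result describe completers only. Early stoppers have no routine scheduled symptom check between their last session and the optional month-6 visit, except the motor retest after motor decline. The primary tolerability endpoint is not limited to completers.

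One uncalled stopper can move a 60% interest result by at most about 5.5 percentage points, and two by at most 10. The effect is nil if nobody stops early. These sizes rest on assumed counts; the documents project no early-stop rate. The conclusion also assumes that the unsupplied sections do not already schedule the call. The change is worth making because it is cheap and the result feeds the next trial's design.

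**What to change.** - **Sections 10.1 and 10.2.6:** give one common anchor for the call, namely one week after the last session attended, whether or not day 5 was reached.
- **Section 8.7:** keep the existing data-retention rule for families who withdraw consent. Add that children who stop sessions early without withdrawing consent are offered the 1-week call, and that its data are used.
- **Reporting:** give the 1-week feedback and the Aim 3 interest proportion over all children who started a session, with early stoppers and non-responders shown separately.
- **If an early termination visit is described elsewhere:** cross-refer to it in the calendar and make it consistent with the above.

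The cost is some protocol wording and one phone call per early stopper, using the existing survey. Some families will decline, so the gap may be reduced but not closed; showing non-responders makes what remains visible.

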10.2 Overview of Study Procedures

Individuals who respond as being interested in the study will be scheduled for a phone or video call to discuss study procedure. At this point we will evaluate whether the family has appropriate computer/ internet access. If the family (e.g. parent/caregiver and child) are interested in participating, we will proceed to performing consent/assent via phone call or video conference. As we will request for photos/video of electrode placement, a photo/video authorization form will also be required. We will request for permission to record the videoconference call via the consent form. Following these enrollment procedures, the parent/legal guardian – henceforth referred to as 'caregiver' throughout the protocol- will be asked to participate in a pre-visit which may occur in the same visit as the enrollment. If the participant is an adult with consent capacity (between the ages of 18-21) both the adult and the parent of that adult will be involved in the call. During the pre-visit, an address for the safety monitor study team member, and videoconferencing times will be scheduled for completion of the five-day study. There are two types of sessions that will occur throughout the study (practice and active stimulation). A trained study team member will be present via videoconference with the caregiver/child during the entirety of the sessions. A study team member will be on-site, in-home during active device use to solely ensure safety of the participant. Unless indicated for safety, the safety monitor will not provide guidance in setting up the device or delivering tDCS to the participant. The protocol for survey's, questionnaires, and assessments are detailed below.

